3. AIMS AND OBJECTIVES

3.1 Primary Objective

To evaluate the mean change in ETDRS visual acuity at 48 weeks and 104 weeks from Day 0.

3.2 Secondary Objectives

To evaluate the total number of intravitreal injections required during a 104 week study period (laser versus non laser). To evaluate the percentage of patients with persistent macular edema based on SD-OCT at 48 weeks and 104 weeks.

4. OUTCOMES

4.1 Primary Outcomes

• Mean change in ETDRS visual acuity at week 48 and week 104 from day 0.

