All cohorts will enter a treat and extend protocol for IVT ranibizumab retreatment beginning at week 52. At any visit where a dry macula is achieved din the study eye, the visit interval between IVT ranibizumab treatments will be lengthened by 1 week. A dry macula is defined as the resolution of recurrent or persistent fluid based on SD-OCT, slit lamp examination, and/or indirect ophthalmoscopy.

After a subject has been extended beyond a monthly visit interval between IVT ranibizumab treatments, the visit interval will be reduced by 1 week, if the study eye develops recurrent disease activity. Recurrent disease activity is defined as recurrent or persistent fluid based on SD-OCT, slit lamp examination, and/or indirect ophthalmoscopy.

IVT ranibizumab treatment will be administered in the study eye at every visit, no earlier than 7 days before the target date and no longer than 7 days after the target date. The visit interval between IVT ranibizumab treatments is individualized based on each patient's response to treatment. The visit interval between IVT ranibizumab treatments will not exceed 12 weeks.

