2.1 Sample Size Calculations

A priori power calculation was performed and revealed that a sample size of n=41 was needed to achieve 80% power using single factor ANOVA with a significance level (alpha) of 0.05. Based on this result, the final study size was 40. Patients randomized in a 1:2:2 ratio. Sample size estimation was performed using RStudio (Version 1.1.463, RStudio Inc., Boston, Massachusetts). Statistical analyses were performed using Prism (GraftPad Software, San Diego, CA) and the data analysis function in Microsoft Excel (Microsoft Inc., Redmond, WA).

The reason for the 1:2:2 randomization ratio was that the monthly group would have less variability in terms of treatment course because each patient would receive an injection each month without alterations or additional factors to their treatment regimen, allowing for detection of the group's trend with a smaller cohort size. On the other hand, the other two cohorts could have different treatment schedules and therefore would require more patients to capture the trend. The exception to this randomization was that patients whose central vision of 20/50 or better at screening exam were randomized into the three cohorts in a 1:1:1 ratio in order to minimize a disproportionate population of subjects with good vision in any one group and to minimize the chance of significant difference in baseline vision between groups. Randomization occurred on Day 0 in which a randomly selected envelope containing a cohort assignment was chosen for each patient.

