6. ANALYSES

All outcomes will be presented using descriptive statistics. For comparison of groups for primary and secondary outcomes, variables of interest will be statistically analyzed using analysis of variance (ANOVA), Student's t-tests, Chi square and Fisher's exact test. ETDRS data will be obtained for all visits

for all 40 of the participants. Bonferroni correction was applied to all pairwise comparison analyses for this study.

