6.1 Primary Outcome

The primary analysis will compare cohorts (A vs. B vs. C) on their mean change in ETDRS BCVA from baseline to week 48 and week 104 with the above described statistical tests. Adverse events will be reported using counts and percentages for each cohort.

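### Week 48 and week 104 are both primary, with no order, alpha split or success rule, while the trial is sized for one ANOVA at 0.05

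*SAP*

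**What the plan says.** SAP 4.1 gives the primary outcome as "Mean change in ETDRS visual acuity at week 48 and week 104 from day 0", and SAP 3.1 gives the objective as "To evaluate the mean change in ETDRS visual acuity at 48 weeks and 104 weeks from Day 0". Protocol 2.1, 3.3.1 and 4.8.3.1 name the same two weeks. Under SAP 6.1 the plan is to "compare cohorts (A vs. B vs. C) on their mean change in ETDRS BCVA from baseline to week 48 and week 104", using the tests listed in SAP 6: ANOVA, t-tests, chi-square and Fisher's exact test, none assigned to a particular endpoint or week.

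On size, SAP 2.1 reports that "a sample size of n=41 was needed to achieve 80% power using single factor ANOVA with a significance level (alpha) of 0.05", and then "Based on this result, the final study size was 40". It gives no effect size, no standard deviation and no week.

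On multiplicity there is one sentence, in SAP 6: "Bonferroni correction was applied to all pairwise comparison analyses for this study". The same section opens by saying that every outcome will be summarised descriptively.

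Neither document ranks the two weeks, shares alpha between them, or states what combination of results counts as a primary finding.

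**The concern.** The plan specifies two primary comparisons and a power calculation for one. If the cohorts differ at one week and not at the other, nothing in the documents says what the trial found, and the rule could be settled after the results are known.

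The two weeks could well differ. The cohort-specific injection schedules and the laser sessions fall within the first 48 weeks, after which "All cohorts will enter a treat and extend protocol for IVT ranibizumab retreatment beginning at week 52". An effect present at week 48 may have faded by week 104, or one may appear only later.

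At stake are the clarity of the primary conclusion and, under one of the possible readings, the stated 5% error rate.

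**Working it through.** **Inputs from the documents.** Three cohorts planned at 8/16/16; N=41 required and 40 taken; alpha 0.05; power 80%; single-factor ANOVA (SAP 2 and 2.1).

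**Assumptions.** ANOVA as the primary test is inferred from SAP 2.1 and the three-cohort comparison in SAP 6.1. The correlation rho between the week 48 and week 104 changes is not given, so it is varied from 0 to 0.95. Data are complete and normal.

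**1. The plan's own figure.** N=41 cannot be rebuilt, because no effect size is given. It can be inverted. For a one-way ANOVA with 3 groups, power = P(F' > F_crit), with F' noncentral F on 2 and N-3 degrees of freedom and noncentrality f² × N.
- N=41, power 80%: f = 0.5045 (0.5045² × 41 = 10.44; critical F on 2 and 38 df = 3.245).
- N=40, same f: 0.5045² × 40 = 10.18; power 78.9% at alpha 0.05 and 69.0% at alpha 0.025.

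**2. False-claim rate with no true effect, each week tested at 0.05.** At rho=0, either week significant: 1 - 0.95² = 9.75%; both: 0.05² = 0.25%. Other values are simulated (1,000,000 trials per rho).

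**3. Disagreement with f = 0.5045 at both weeks.** At rho=0: 2 × 0.7886 × 0.2114 = 33.3%. Other values are simulated (500,000 trials per rho).

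| rho | Null: either week significant | Null: both significant | f=0.5045: exactly one significant | f=0.5045: both significant |
|---|---|---|---|---|
| 0 | 9.7% | 0.2% | 33% | 62% |
| 0.5 | 9.2% | 0.8% | 24% | 67% |
| 0.7 | 8.5% | 1.5% | 19% | 69% |
| 0.9 | 7.2% | 2.8% | 11% | 73% |
| 0.95 | 6.6% | 3.4% | 8% | 75% |

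**4. Which rho is plausible.** Both changes subtract the same Day 0 value. If acuity at the three visits has equal variance s² and equal correlation r, the covariance of the two changes is s²(1 - r) and each variance is 2s²(1 - r), so rho = 0.5. Zero is therefore an unlikely value, and 0.5-0.9 is the more realistic range: 11-24% disagreement.

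**5. Sensitivity.** Over rho 0-0.95, disagreement is 11-49% at f=0.40 and 4-16% at f=0.60. If the effect (f=0.5045) exists at one week only, disagreement is about 76%.

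**6. Candidate rules.** Under Holm (smaller p-value against 0.025, the other against 0.05):
- overall error with no effect: 3.4-5.0%;
- power per week if both weeks have the effect: 73-76%;
- power if only one week has it: 69%.

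Under a fixed sequence, each test at 0.05:
- power for the first week: 79%;
- power for the second week: 62-75% if both have the effect, about 4% if only the second does.

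**The case against.** The strongest reply is that this is a 40-subject phase II trial with no stated hypothesis or success criterion. SAP 6 promises descriptive presentation, and Protocol 3.3.1 even labels the measure as one of safety and tolerability. On that view, different results at the two weeks are simply two estimates to report. This stands in part and limits the severity. It does not remove the gap, because SAP 2.1 sets an alpha and a power, and SAP 6.1 plans a primary comparison between cohorts.

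A second reply is that Bonferroni already covers the problem. For pairwise claims it may. If it spans all six primary pairs (three at each week), the chance of any false pairwise claim is 4.5% / 4.0% / 3.1% at correlation 0 / 0.7 / 0.95. With three pairs per week it is 8.6% / 7.6% / 5.9%. The sentence does not define its family. On either reading, the overall A vs B vs C comparison is not pairwise, and the sentence cannot say what is concluded when the weeks disagree.

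A third reply is that the disagreement figures rest on inputs the documents do not contain. That is correct. The effect size is only what n=41 and 80% power imply, and nothing ties it to acuity at a particular week. Group sizes may depart from 8/16/16, because subjects at 20/50 or better are randomized 1:1:1 (Protocol 4.2). Protocol 4.8.4 uses available cases, so week 104 may have fewer subjects, although SAP 6 expects data from all 40. The textual gap depends on none of these figures.

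**Conclusion.** The concern holds as a gap in the decision rule. Two weeks are primary, one test was sized, and no rule connects them. The false-claim rate is about 6.6-9.8% if either week suffices at 0.05 and does not exceed 5% if both are required; the documents adopt neither. With f of about 0.50 at both weeks, groups of 8/16/16 and complete data, exactly one week is significant in about 11-24% of trials at correlation 0.5-0.9.

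Two stronger inferences are tempting. A reader might infer that the trial runs at nearly 10% type I error; that needs an either-week rule, which the plan does not state, and correlation near zero. A reader might also infer that up to a third of such trials would end without a conclusion at the planned effect; the documents state no planned effect, and the 33% figure again needs zero correlation. The supported conclusion is narrower: the primary conclusion is undefined when the weeks disagree, which should be settled but does not invalidate the trial.

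**What to change.** In SAP 4.1 and 6.1, and to match in Protocol 2.1, 3.3.1 and 4.8.3.1, name the primary test and state one rule that holds the two primary comparisons at 0.05 overall.

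- **Holm over the two weeks** needs no ordering and lets either week succeed alone. Power per week falls from 79% to 73-76% if both weeks have the effect, and to 69% if only one does.
- **A fixed sequence with a named first week** is acceptable if the sponsor accepts that the second week cannot then succeed alone. The first week keeps 79%. The order is a substantive choice: the cohort-specific regimens run to week 48, while follow-up and the injection-count objective run to week 104.

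SAP 2.1 is written in the past tense, so first record whether outcome data had been seen when the rule is chosen. If they had, label the rule post hoc and report both weeks in full with confidence intervals; a rule chosen then does not restore error control.

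Leave the existing Bonferroni correction for pairwise comparisons in place. Relaxing it to three pairs per week behind an ANOVA gate would be a separate change, and its false pairwise rate reached 5.3% in the worst case simulated (very large effect at week 48 only, correlation 0).

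Apart from the power given up, the cost is text in both documents: no new data and no change in sample size.

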4.2 Secondary Outcomes

• The mean number of intravitreal injections required per subject per cohort.

- Percentage of subjects with persistent macular edema, based on SD-OCT, at week 48 and week 104 compared to day 0.
- Percentage of subjects avoiding the development of neovascular glaucoma and/or vitreous hemorrhage.

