2.2. SECONDARY OBJECTIVES

- Total number of intravitreal injections required during a 104 week study period (laser versus non-laser)
- Percentage of patients with persistent macular edema based on SD-OCT at 48 weeks and 104 weeks.

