3.4. SAFETY PLAN

The safety assessments to be conducted for this study are listed in Section 4.5.

The safety and tolerability of intravitreal ranibizumab injections have been investigated in previous Phase I, I/II, III, and IIIb studies in AMD, RVO, and DME trials. Potential safety issues associated with the route of administration or the pharmacology of ranibizumab in the study population include decreased BCVA, intraocular inflammation, intraocular infection, transient and/or sustained elevation of intraocular pressure (IOP), cataract development or progression, retinal or intravitreal hemorrhage, macular edema, retinal break or detachment, and arterial thromboembolic events (ATEs). Safety will be assessed by visual acuity, ophthalmic examinations, fluorescein angiograms, B-Scans, OCT, intraocular pressure, vital signs, and adverse event documentation.

To minimize the risks of intraocular infections, all injections will be performed employing sterile techniques as described in Appendix B. Study drug administration will be held for subjects who experience certain ocular events or infections. In the event any subject develops an adverse event in the study eye that is considered by the evaluating physician to be severe in intensity, serious consideration should be given to withdrawing the subject from the study.

The PI or designated Sub-Investigators will review all adverse events on an ongoing basis to determine causality and relationship to study drug and/or study procedures.

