4.8.4. Missing Data

Analyses of efficacy and safety will be based on available cases, without imputation for missing values.

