4.3 Safety Outcomes

The safety and tolerability of intravitreal ranibizumab have been investigated in previous Phase I, I/II and III studies in AMD, RVO, and DME trials. Potential safety issues associated with the route of administration or the pharmacology of aflibercept in the study population include decreased BCVA, intraocular inflammation, intraocular infection, transient and/or sustained elevation of intraocular pressure (IOP), cataract development or progression, retinal or intraretinal hemorrhage, macular edema, retinal break or detachment, and arterial thromboembolic events (ATEs). Safety will be assessed by visual acuity, ophthalmic examinations, fluorescein angiograms, SD-OCT, intraocular pressure, vital signs, and adverse event documentation.

To minimize the risks of intraocular infections, all injections will be performed employing sterile techniques. Study drug administration will be held for subjects who experience certain ocular events or infections. In the event any subject develops an adverse event in the study eye that is considered by the evaluating physician to be severe in intensity, serious consideration should be given to withdrawing the subject from the study.

The PI or designated Sub-Investigators will review all adverse events on an ongoing basis to determine causality and relationship to study drug and/or study procedures.

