6.2 Secondary Outcomes

The secondary analysis will compare cohorts (A vs. B vs. C) on their mean CMT measurements at baseline, week 48 and week 104. The secondary analysis will also compare percentage of eyes with intraretinal exudates, retinal hemorrhage, and neovascularization at baseline, week 48 and week 104. The frequency of injection will be compared between cohorts and the correlation between injection frequency and CMT and/or ETDRS BCVA will be assessed.

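### The injection-burden outcome is a count with no allowance for time in study, and the plan does not say how withdrawn subjects or held doses enter it

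*SAP*

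**What the plan says.** Lowering the injection burden is a stated purpose of the trial (Protocol 3.2, SAP 2). The outcome that measures it is "The mean number of intravitreal injections required per subject per cohort" (SAP 4.2, with the same wording in Protocol 3.3.2 and 4.8.3.2). The objective in Protocol 2.2 and SAP 3.2 is a total over the 104-week study, laser against non-laser. SAP 6.2 states: "The frequency of injection will be compared between cohorts and the correlation between injection frequency and CMT and/or ETDRS BCVA will be assessed". It does not say whether frequency means a count or a rate. SAP 6 lists ANOVA, t-tests, chi-square and Fisher's exact test for primary and secondary outcomes, without assigning one to this outcome.

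On incomplete data, Protocol 4.8.4 says: "Analyses of efficacy and safety will be based on available cases, without imputation for missing values".

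Both documents foresee interrupted treatment. Protocol 3.4 says: "Study drug administration will be held for subjects who experience certain ocular events or infections". For severe study-eye events, SAP 4.3 says "serious consideration should be given to withdrawing the subject from the study". Protocol 4.5.2 and 4.6 provide for early termination. I found no follow-up-time denominator, offset, completer restriction or rule for scoring a held dose.

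**The concern.** A subject who leaves early still has an injection count, but it covers only part of the period. If that count goes into a simple mean, the missing months look like months in which no injection was needed. The reason for leaving can make this worse: Protocol 4.6 lists the need for a different anti-VEGF agent as a ground for discontinuation, so an eye that still needs treatment would stop adding to its count.

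The A versus B comparison is the most exposed. Both cohorts follow the same monthly schedule to week 48, so in that period their counts can differ only through withdrawals, holds or missed visits. The information on whether laser lowers need in A versus B comes from week 52 onward, which early leavers do not supply. At stake is whether a difference in mean injections reflects treatment or retention.

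**Working it through.** The plan gives no figure for this outcome to reproduce. Its one computed design figure, n=41 in SAP 2.1, is not tied to injections and states no effect size. The counts below come from the documents' schedule.

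**Inputs.** Cohort sizes 8/16/16 and dosing every 28 days to week 48 in A and B (SAP 2). One-week extensions from week 52, capped at 12 weeks, through week 101 (SAP 2).

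**Assumptions.** The first extension is from 4 to 5 weeks. Week 12 is an injection visit in A and B. No extra injection is added for the mandatory week-78 visit on the never-dry path. The number and timing of withdrawals are illustrative.

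**Counts for a completer**
- Day 0 to week 48, A and B: weeks 0, 4, ..., 48 = 13.
- Weeks 52 to 101, always dry: 52, 57, 63, 70, 78, 87, 97 = 7.
- Weeks 52 to 101, never dry: 52, 56, ..., 100 = 13.
- Total in A or B: 13 + 7 = 20 to 13 + 13 = 26. In C: 3 + 7 = 10 to 13 + 13 = 26.

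**Shift in the raw mean if partial counts are kept** (shift = injections lost / n)

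| Event in one subject | Injections lost | Cohort A (n=8) | Cohort B (n=16) |
|---|---|---|---|
| Leaves after week 24 (count 7) | 20−7=13 to 26−7=19 | 1.63 to 2.38 | 0.81 to 1.19 |
| Leaves at week 76 (count 17 or 20) | 20−17=3 to 26−20=6 | 0.38 to 0.75 | 0.19 to 0.38 |
| One held dose | 1 | 0.125 | 0.06 |

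**Direction, with equal true need of 20 in A and B**
- Two week-24 leavers in B, none in A: B = (14×20 + 2×7)/16 = 18.4 against A = 20.0, a spurious difference of 1.6 (2.4 if need is 26).
- One in A, none in B: A = (7×20 + 7)/8 = 18.4 against B = 20.0. The non-laser cohort now looks lighter by 1.6.
- One of 8 in A and two of 16 in B: both means are 18.4, difference 0.

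**Which rate removes the problem**
- Single whole-study rate: the week-24 leaver scores 7/24 weeks = 1.17 per 4 weeks; a completer scores 20/104 = 0.77 to 26/104 = 1.00. This overcorrects.
- Per-subject rate within weeks 52 to 101, always-dry eyes: a week-63 leaver has 3 in 11 weeks = 1.09 per 4 weeks; a completer has 7 in 49 = 0.57. With one such leaver among 16, the mean of the rates is (15×0.571 + 1.091)/16 = 0.604, about 6% too high.
- Pooled rate, same 16 eyes: (15×7 + 3)/(15×49 + 11) = 108/746 = 0.1448 per week against 7/49 = 0.1429, about 1% too high. The raw mean is 108/16 = 6.75 against 7, about 4% too low.
- Pooled rate to week 48, one week-24 leaver among 8 in A: (7×13 + 7)/(7×48 + 24) = 98/360 = 0.2722 against 13/48 = 0.2708, about 0.5% too high. The raw mean is 98/8 = 12.25 against 13, about 6% too low.

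**The case against.** The strongest reply is that the documents never say a truncated count enters the mean. The objective is a 104-week total, and a subject who left at week 24 has none, so the available-case rule could equally mean that the subject is dropped. The outcome concerns injections required, so a held dose is unclassified rather than scored as unneeded. SAP 6.2 may intend a rate. These points stand: a reader might infer that every withdrawal and every hold is counted as lower need, and the documents do not establish that. What they leave is a choice between count and rate, and between keeping and dropping leavers, that could be made after the data are seen. Dropping leavers also excludes those who left for cause and does not settle how held doses count.

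A reader might also infer that the bias always runs towards the laser cohorts. It does not: one loss in A weighs twice one in B or C and makes the non-laser cohort look lighter.

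Third, two week-24 leavers in B shift its mean by 1.6 to 2.4, and it is tempting to set that against the 6-injection range between always-dry and never-dry eyes (27 to 40%). That mixes periods, because 2×6/16 = 0.75 of the shift is lost before week 52. Losses from week 52 alone are 2×7/16 = 0.88 to 2×13/16 = 1.63, or 15 to 27% of the range.

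Finally, any rate inherits some front-loading. In Cohort C, a subject leaving at week 12 after three loading doses scores 1.0 per 4 weeks, against 0.42 for a completer with, say, 5 injections in 48 weeks. This is a reason to pool and to split by period; it does not rescue the raw mean.

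**Conclusion.** The point holds as a gap in definition with a material consequence under one permitted reading. The outcome is a count, nothing adjusts it for follow-up, and the plan does not say how withdrawn subjects or held doses are treated. If partial counts are kept, the comparison favours whichever cohort loses more follow-up, and a single week-24 withdrawal is enough to move the Cohort A mean by 1.6 to 2.4 injections. Later exits matter less, proportionate losses cancel, and isolated held doses are minor.

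The sizes rest on the planned 8/16/16 split, which the 1:1:1 allocation of subjects with 20/50 or better vision may alter, and on assumed withdrawals. This is a secondary outcome, but it is the one that measures the trial's stated aim of fewer injections, so it should be settled before analysis.

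**What to change.** In SAP 4.2 and 6.2:

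- Analyse injections separately for Day 0 to week 48 and for weeks 52 to 101, and state when each subject's follow-up time starts and stops.
- In each period compare cohorts on the pooled rate, total injections over total follow-up time. A Poisson-type model with cohort as the factor and log follow-up time as offset gives this. Use a robust or quasi-likelihood variance, because counts in A and B to week 48 are nearly fixed by schedule and a Poisson variance would be too large.
- Do not use per-subject annualised rates or a single whole-study rate: injections are front-loaded, and early leavers would look needier.
- Show the raw mean count in period completers as a sensitivity analysis.
- Report the number of held doses by cohort, apart from doses not required.

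The cost is SAP wording and one model per period, using injection and visit dates. The result becomes a rate by period rather than one simple mean, and some front-loading bias remains in the treat-and-extend period and in Cohort C's loading phase. With only eight subjects in Cohort A, the robust standard error should carry a small-sample correction.
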